### **Definition of Major Response and “Stopping Rule”:**

A major response is defined by any of the following serious adverse events occurring during the study period. It serves as the “stopping rule” as detailed in the **Figure 4** above.

- Second degree scalp burn at the site of electrode pad; or
- Seizure; or
- New lesion(s) on DWI sequence of MRI scan and the lesion(s) is not explained by any other cause(s) or decreased ADC under the electrode stimulating motor cortex area; or
- Patient discontinues from the study due to any reasons above.

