#### Aim 1: To determine the optimal current in stroke patients

##### D1.1 Design:

This aim is a phase I type study to determine the most efficacious current for tDCS, recognizing that this current level must be tolerable and safe. The trial design is adapted from the classical, gold-standard 3+3 drug trial design, which is commonly used to find the maximal tolerable dose for a chemical drug. The main justification for this design is that the maximal tolerable current (dose) is usually and arbitrarily defined as the dose at which one-third of the patients experience current (dose)-limiting major side effects/response. The algorithm for current (dose) escalation is detailed in (**Figure 4**). The study starts with 1 mA : (a) if no major response occurs in any of the three subjects, a next current at 2 mA will be used next; (b) if major response occurs in 2-3 study subjects, then the trial will stop at this current level; (c) if major response occurs in one subject, then 3 additional study subjects will be entered to further test the safety of same current dose; if no major response occurs, then the current will be escalated next current level; if further major response occurs, then the trial will terminate. The previous current level will be defined as the maximal tolerable current (dose). The current tDCS device available on the market (Chattanooga Dual-Channel Iontophoresis Device) for research use has a maximal current of 4.0 mA. The sequence for current escalation will be 1.0 mA >> 2.0 mA >> 2.5 mA >> 3.0 mA >> 3.5 mA >> 4.0 mA.

While we vary current in this protocol, other features of the stimulation will be controlled:

- **Duration of stimulation will be 30 minutes:** Data show the increased excitability of tDCS can last as long as 90 minutes. Our rehabilitation intervention will take one hour. Thus, by using 30 minutes of

stimulation, as has been commonly used in stroke studies, we should ensure that the potentially beneficial effects of the stimulation will not wear off during the course of rehabilitation.

- **Size of electrode will be 3 × 5 cm^2:** The commonly used 3 × 5 cm^2 size pad is chosen because it is adequate to cover the the primary motor cortex – our area of interest for brain stimulation in stroke subjects to facilitate upper extremity motor function recovery.

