25. Note that these analyses must be completed for each set of 3 subjects in a group to determine whether one or more major responses occurred before enrollment continues. If no major response occurs, the next 3 subjects will be entered to go through procedure 9-23 according to **Figure 4**.

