### **D1. 4. Anticipated Results:**

We anticipate that 4.0 mA will be tolerable and safe both at clinical and subclinical levels, as evidenced by a lack of major responses in the study subjects. In addition we expect that 4.0 mA will produce the largest increase in MEPs amplitude compared with other current levels.

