#### **tDCS Protocol:**

Direct current stimulation will be delivered to the study subjects through 2 saline-soaked EasyPad (3cm \* 5cm=15cm^2) using a Chattanooga Dual-Channel Iontophoresis Device (Chattanooga Medical. Inc). For this protocol, the bihemispheric stimulation montage will be used because a safety profile can be evaluated for both anodal stimulation and cathodal stimulation on the same subject. The anodal stimulation will be placed over the ipsi-lesional and the cathodal over the contra-lesional motor cortex (C3 and C4 areas by using the international 10 –20 EEG electrode systems). Electrode pads will be disposed after each stimulation session. During the middle of stimulation, an inspection of electrode pads will be conducted to make sure they have not dried out, and the scalp temperature will be measured using a touchless thermometer. Stimulation will last for 30 minutes. Thus, subjects will perform for thirty minutes with stimulation and 30 minutes after it has ended. The QBAR core therapist will be blinded to dosage and montage of stimulation by the BSTIM core technician. The experiment will be conducted in the Upper Extremity Function Laboratory of the Center for Rehabilitational Research in Neurological Conditions (**QBAR core**).

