### **Protection to Human Subjects:**

#### **tDCS:**

- 1) Strictly follow the inclusion and exclusion criterias
- 2) Study part 1 is a tolerabilty study. Adverse events are recorded carefully on every visit on every patients, if major response occurs, DSMB will be notified immediately.

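### The Aim 1 escalation rule cannot register a subject who stops for intolerable discomfort, yet its result is called the maximal tolerable current

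*Combined protocol and SAP*

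**What the plan says.** The definition of a major response in D1.1 opens with "A major response is defined by any of the following serious adverse events occurring during the study period". Three harms follow: a second-degree burn under a pad, a seizure, and a new unexplained DWI lesion or reduced ADC beneath the electrode. The fourth item is "Patient discontinues from the study due to any reasons above".

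Escalation depends on this count alone. D1.1 escalates after 0 of 3 and stops after 2 or 3 of 3. After 1 of 3 it adds three subjects, then escalates only if none of them has a major response. D1.2 requires the results of each set of three to be analysed "to determine whether one or more major responses occurred before enrollment continues".

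The conclusions are worded in terms of tolerability:

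- D1.1 seeks the most efficacious current, "recognizing that this current level must be tolerable and safe".
- When the trial stops, "The previous current level will be defined as the maximal tolerable current (dose").
- D1.4 expects 4.0 mA to be "tolerable and safe both at clinical and subclinical levels, as evidenced by a lack of major responses".
- The human-subjects section states: "Study part 1 is a tolerabilty study".

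The tDCS Protocol fixes the exposure: "Stimulation will last for 30 minutes". Symptoms such as headache, burning and tingling are collected by questionnaire (D1.2), and safety measures are summarised descriptively by current group (D1.3).

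**The concern.** The fourth item looks like the place where intolerance would enter the rule, but it is restricted to reasons that already count. The rule therefore measures freedom from a short list of serious harms, while the plan reports its result as tolerability. Followed exactly, it can escalate past a current that subjects could not complete for 30 minutes, and can call that current tolerable.

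Four of the six levels exceed 2 mA, and the human-subjects section acknowledges possible side effects above that current. The current determined in Aim 1 is carried into Aim 2 (Specific Aims) and into the planned Phase II trial (D5.4), so the basis for calling it tolerable matters beyond this study.

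**Working it through.** **Reproducing the plan's figures.** The sequence 1.0, 2.0, 2.5, 3.0, 3.5, 4.0 mA has six levels. The minimum is 3 subjects, the maximum is 6 × 6 = 36, and with no major response 6 × 3 = 18. These match D1.3 (3 to 36, with 18 predicted).

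**Is the fourth item redundant?** Let B, S and M be the burn, seizure and MRI events, and D discontinuation. Without the fourth item, a major response is (B or S or M). With it, a major response is (B or S or M) or [D and (B or S or M)]. The bracket can be true only when the first part is already true. All 16 combinations of B, S, M and D are classified identically under both forms.

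**Consequence with no assumed rate.** Suppose all three subjects in a set stop for pain and none has a burn, seizure or MRI change. The set scores 0 of 3 and the current is raised. With no listed event at any level, the rule clears all six levels in 18 subjects, whether 0 or 18 stopped early.

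**Consequence if such stops counted.** The available text gives no rate of stopping for discomfort, so the rates p below are assumptions. Take independent subjects, no listed serious event, and q = 1 − p.

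- P(level cleared) = q³ + 3pq² × q³
- P(level needs three more subjects) = 3pq²

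| Assumed p | Cleared, as written | Cleared, if stops count | Needs 3 more |
|---|---|---|---|
| 0.05 | 1.00 | 0.8574 + 0.1354 × 0.8574 = 0.973 | 0.135 |
| 0.10 | 1.00 | 0.729 + 0.243 × 0.729 = 0.906 | 0.243 |
| 0.20 | 1.00 | 0.512 + 0.384 × 0.512 = 0.709 | 0.384 |
| 1/3 | 1.00 | 0.2963 + 0.4444 × 0.2963 = 0.428 | 0.444 |

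One-third is the benchmark D1.1 itself uses for the maximal tolerable dose, although there it refers to major side effects. At that rate escalation would stop at the level with probability 1 − 0.428 = 0.572 if stops counted, and 0 as written.

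**Whole trial if stops counted.** Expected enrolment is the sum over levels of P(level reached) × (3 + 3 × 3pq²).

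- *p = 0.20 at 3.5 and 4.0 mA only.* P(4.0 mA cleared) = 0.7086² = 0.502. Expected enrolment = 12 + 4.152 + 0.7086 × 4.152 = 19.1.
- *p = 0.10 at all six levels.* P(4.0 mA cleared) = 0.9061⁶ = 0.554. Expected enrolment = 3.729 × (1 + 0.9061 + … + 0.9061⁵) = 3.729 × 4.756 = 17.7.
- *Rates rising across the six levels.* With 0/0/5/10/15/20%, P(4.0 mA cleared) is 0.51 and expected enrolment 19.5. With 0/5/10/20/30/40% the figures are 0.10 and 17.7.

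**Precision per level.** For 0 of 3, the exact two-sided 95% upper limit is 1 − 0.025^(1/3) = 0.708, or 71%.

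**The case against.** The strongest reply is that the restriction is deliberate. The list is headed as serious adverse events, section A3 treats local symptoms as a minor matter, and D1.1 ties the one-third benchmark to major side effects. D1.3 records that the DSMB advised taking S-100 and NSE out of the stopping rule, so its content had been considered. A 3+3 result is always relative to the events it counts. This may well be so, but then the word *tolerable* is what is wrong, because a rule limited to serious harms cannot support it.

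Tolerability is also examined by other means: questionnaires, a mid-session pad check with scalp temperature, adverse-event recording at every visit, tables by current, and a DSMB that may advise changes. Aim 1 describes the optimal current as a balance of excitability and tolerability. All of this stands as judgement, but none of it is tied to escalation. The DSMB's stated triggers for notification or an early meeting are themselves major responses or stopping-rule events. Otherwise it meets every 6 months. At the planned 2 to 3 subjects per month (D5.1), 12 to 18 subjects, or four to six sets of three, could be treated between meetings.

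Two points stand and limit the size of the problem. First, the maximal tolerable label in D1.1 is attached when the trial terminates for major responses. If no listed event occurs, only D1.4 calls 4.0 mA tolerable. Second, if the true rate of discomfort stops is near zero, escalation is essentially unchanged.

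Figure 4 was not visible, but D1.1 spells out its algorithm in words.

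**Conclusion.** The concern holds and should be fixed. The fourth item adds no event, the rule is blind to stopping for discomfort, and the plan still draws a conclusion about tolerability from it. That is a matter of logic and needs no assumed rate. The practical size depends on the unknown rate of such stops: at assumed rates from 5% to one-third, the chance of clearing a level would fall from 1.00 to between 0.973 and 0.428 if they counted. These figures assume independent subjects and no listed serious event.

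Two gaps follow. Table 2 and the stimulation-day steps have no item for whether the 30 minutes were completed. Nor does the plan say whether a subject who stops early counts in the set of three or is replaced.

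**What to change.** There are two options.

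1. **Make the rule test tolerability.** Replace the fourth item with: *stimulation is stopped before 30 minutes, or the subject withdraws, because of a stimulation-related symptom the subject cannot tolerate*. Agree this with the DSMB before the first set is enrolled, and count such subjects in the set of three without replacement.
2. **Keep serious harms only.** Rename the output in D1.1 and D1.4 as *the highest current without a listed serious adverse event*.

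In either case, record completion of stimulation and the reason for stopping, and report both by current with exact confidence limits, noting how wide they will be.

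The first option costs protocol wording, DSMB agreement and one data item, but it also changes the operating characteristics. Even 10% intolerance at every level would keep 4.0 mA from being cleared with probability 1 − 0.554 = 0.446. Expected enrolment in the two cases with a single assumed rate (17.7 and 19.1) stays close to the planned 18 and within 3 to 36. The second option costs only the wording and the data item, and leaves escalation unchanged.

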### **Inclusion Criteria:**

Each subject must meet **all** of the following criteria to participate in this study.

- 18-80 years old with a first-ever ischemic stroke that occurred at least 6 months ago;
- Finished rehabilitation therapy(including inpatient or outpatient PT/OT/SP) at least one month ago;
- Unilateral limb weakness with Fugl Meyer-Upper Extremity Scale score less than or equal to 58 (out of 66);
- MEPs is inducible on abductor pollicis brevis (APB) muscle on the affected side by TMS.

### **Exclusion Criteria:**

Subject who meets **any** of the following criteria will be excluded from the study.

- Primary intracerebral hematoma, or subarachnoid hemorrhage,
- Bihemispheric ischemic strokes;
- History of prior stroke or old infarct demonstrated on the CT or MRI or documented in medical records;
- Other concomitant neurological disorders affecting upper extremity motor function;
- Documented history of dementia before or after stroke;
- Documented history of uncontrolled depression or psychiatric disorder either before or after stroke which could affect their ability to participate in the experiment;
- Uncontrolled hypertension despite treatment, specifically SBP/DBP $\geq$ 180/100mmHg at baseline;
- Presence of any MRI/tDCS/TMS risk factors: a) an electrically, magnetically or mechanically activated metal or nonmetal implant including cardiac pacemaker, intracerebral vascular clips or any other electrically sensitive support system; b) non-fixed metal in any part of the body, including a previous metallic injury to eye; c) pregnancy, since the effect of tDCS on the fetus is unknown; d) history of seizure disorder or post-stroke seizure; e) preexisting scalp lesion, bone defect or hemicraniectomy.

### **D1. 2. Recruitment Process & Procedure:**

A schedule of assessments is presented in **Table 2**.

[figure not shown]
Table 2	Baseline*	Stimulation Day (Day 0)	Follow-up
---------	-----------	-------------------------	-----------

	(Day -7 ± 7)	Pre-stim	Post-stim	(Day 14 ± 4)
Eligibility Determination and Informed Consent	X			
Demographics	X			
Vital Signs and Safety Questionnaire	X	X	X	X
TMS Evaluation	X	X	X	
Laboratory		X	X	X
Brain MRI		X	X	

\* Baseline can be same day as Stimulation Day to facilitate recruitment.

[figure not shown]
[figure not shown]
- **Baseline Day (Total Estimated Time: ~ 2 hours)**

1. Subject reports to the College of Health Professions (CHP) building QBAR laboratory.
2. Subject is consented first, then starts screening process.
3. Vital signs are taken. Urine pregnancy test for subjects of childbearing age. Estimated time is 10 minutes.
4. Demographics collected, including age, ethnicity, gender, time from stroke (in months), side of infarct, handedness, medical history and medication list. Estimated time is 20 minutes.
5. A technician from the **BSTIM Core** will perform a **Basic TMS Neurophysiological Assessment** to determine if a MEP is inducible on abductor pollicis brevis (APB) muscle on the affected side by TMS (Details in **BSTIM Core**). Estimated time is 30 minutes.
6. Subject takes structured questionnaire. The questionnaire inquires whether the patient has experienced any of the following symptoms: headache, nausea, burning, tingling, itching, neck pain, electric shock, inattention and etc. It also has open questions inquiring about subject's general impression about the stimulation. Estimated time is 10 minutes.
7. A therapist from the **QBAR Core** will perform **Clinical Assessments** including upper-extremity Fugl-Meyer (UE-FM) scale. Estimated time is 30 minutes.
8. Subjects who meet the inclusion/exclusion criteria are eligible for the study and move to the next step.

- **Stimulation Day (7 days after baseline day; Estimated Time: ~4 hours)**

9. Subject report to Center of Advance Imaging for Research (CAIR). The **NI Core** will perform **structural 3T MRI** (Details in **NI Core and MRI protocol**). Estimated time is 30 minutes.
10. Subject is transported to CHP research building QBAR laboratory (less than 100 yards away).
11. Blood draw is performed collecting 10 ml's and specimen is sent to [name] laboratory in the Children's Hospital. . Urine pregnancy test for subjects of childbearing age. We have updated the protocol. Estimated time is 10 minutes.
12. Subject takes structured questionnaire survey. Estimated time is 10 minutes.
13. A technician from the **BSTIM Core** will perform a **Basic TMS Neurophysiological**

[figure not shown]

**Assessment** to determine cortical excitability (details in **BSTIM Core and TMS protocol**) in the BSTIM laboratory in the CHP research building (the room next door to the QBAR laboratory).

Estimated time is 30 minutes.

14. Vital signs are taken. Estimated time is 5 minutes.
15. The **BSTIM core** oversees tDCS stimulation protocol. The PI will administer the tDCS under the supervision of the **BSTIM core**.
16. Coincident with the beginning of stimulation, the therapist from the **QBAR Core** begins a one hour **Upper Extremity Rehabilitation** session of patient-targeted upper extremity function therapy (details in **QBAR Core and Therapy Protocol**). Estimated time is 60 minutes.
17. At the end of the rehabilitation session, the technician from the **BSTIM Core** will again perform a **Basic TMS Neurophysiological Assessment** to determine cortical excitability. Estimated time is 30 minutes.
18. The structured questionnaire survey is performed again. Estimated time is 10 minutes.
19. A second blood draw is performed and specimen is delivered to [name] laboratory in the Children's Hospital I. Estimated time is 10 minutes.
20. Subject is transported to CAIR. **NI Core** will again perform **structural 3T MRI** (Details in **NI Core and MRI protocol**). Estimated time is 30 minutes.
21. Patients are advised to call the study team if they experience any untoward side effect before the follow up day.

- **Follow-up day (14 days after stimulation day; Estimated time: ~ 0.5 hour)**

22. Subject reports to CHP research building QBAR laboratory.
23. A blood draw is performed collecting 10 ml's and specimen is sent to [name] laboratory in the Children's Hospital. Estimated time is 10 minutes.
24. The structured questionnaire survey is performed again. Estimated time is 10 minutes.

- **Final analyses:**

25. Note that these analyses must be completed for each set of 3 subjects in a group to determine whether one or more major responses occurred before enrollment continues. If no major response occurs, the next 3 subjects will be entered to go through procedure 9-23 according to **Figure 4**.

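### Step 25's range 9-23 leaves out the Day 14 questionnaire that Table 2 requires, and no step says how the scalp-burn criterion is ascertained after stimulation

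*Combined protocol and SAP*

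**What the plan says.** Aim 1 procedures in D1.2 are numbered 1 to 25. Steps 1-8 are baseline, 9-21 the stimulation day, 22-24 the follow-up day, and 25 the review of each set of three. If that review finds no major response, "the next 3 subjects will be entered to go through procedure 9-23".

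The last follow-up step reads "24. The structured questionnaire survey is performed again". Table 2 has a single row, "Vital Signs and Safety Questionnaire", marked at baseline, before stimulation, after stimulation and at follow-up (Day 14 ± 4), with no exception for any cohort. Aim 1 in the Specific Aims likewise relies on vital signs and a questionnaire around stimulation to judge tolerability.

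The section defining a major response lists "Second degree scalp burn at the site of electrode pad" first among the events that govern escalation. The tDCS Protocol provides a check midway through stimulation: "an inspection of electrode pads will be conducted to make sure they have not dried out", plus a contact-free scalp temperature reading. The questionnaire (step 6, repeated at 12, 18 and 24) asks about "headache, nausea, burning, tingling, itching, neck pain, electric shock, inattention and etc" and includes open questions.

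**The concern.** Two separate things look wrong.

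First, the instruction that staff would follow for later cohorts disagrees with the schedule of assessments. D1.3 plans to summarise safety measures by current group. If Day 14 questionnaires existed only at 1 mA, that comparison could not be made at any current from 2 mA up.

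Second, D1.4 will take the absence of major responses as the evidence that 4.0 mA is safe. That inference is only as good as the ascertainment of each listed event. The imaging criterion has a scheduled scan after stimulation. The burn criterion, a graded skin finding, has no stated examination. The plan itself expects the risk: A3 mentions stimulation-induced skin lesions, and the risk section lists burns under the pads for currents above 2 mA. The current chosen here also feeds Aim 2 and the planned Phase II trial.

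**Working it through.** **1. Step list against Table 2 (Aim 1)**

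| Item | Table 2 | Numbered steps | Within 9-23 |
|---|---|---|---|
| Questionnaire | baseline, pre, post, Day 14 | 6, 12, 18, 24 | 12, 18 |
| Vital signs | baseline, pre, post, Day 14 | 3, 14 | 14 |
| Laboratory | pre, post, Day 14 | 11, 19, 23 | all |
| MRI | pre, post | 9, 20 | all |
| TMS | baseline, pre, post | 5, 13, 17 | 13, 17 |

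The stimulation and follow-up steps run 9-24. Removing 9-23 leaves exactly one, step 24. Vital signs are a different mismatch: steps 3 and 14 both precede stimulation, so no choice of range supplies the two later readings.

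**2. How many subjects the literal range touches**

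D1.1 lists six currents and D1.3 states 3 to 36 subjects, with 18 predicted. These reproduce: stopping after the first cohort gives 3, 6 × 6 = 36, and 6 × 3 = 18. On the predicted path the first cohort (3 subjects, 1 mA) follows the full list, and 18 − 3 = 15 subjects, all at 2 mA or more, come under step 25.

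**3. Where a burn could be noticed**

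- During stimulation: pad dryness and scalp temperature, both before exposure ends.
- After therapy: "18. The structured questionnaire survey is performed again". This records symptoms. A3 lists a burning sensation among the common minor effects, so that answer does not separate sensation from a second degree lesion.
- Between visits: step 21 advises subjects to telephone.
- Generally: the human-subjects section has adverse events recorded at each visit and, under TMS, side effects assessed after each session.

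None of these names a skin examination, an examiner or a grade.

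**4. Direction of any bias**

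With recorded major-response probability p per subject and q = 1 − p, a level is passed with probability

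P = q³ + 3pq² × q³.

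P falls as p rises. Missing an event lowers the recorded p, so it can only raise P.

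The documents do not support a single size. As an illustration, take a true rate of 1/3 (the fraction D1.1 uses to define the maximal tolerable current). Assume a share f of major responses are burn-only, of which a fraction s is detected. All other events are detected. Then p = (1/3)(1 − f + fs). With full detection p = 1/3 and P = 0.296 + 0.444 × 0.296 = 0.43.

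| Burn-only share f | s = 1 | s = 0.5 | s = 0 |
|---|---|---|---|
| 0.25 | 0.43 | 0.51 | 0.60 |
| 0.50 | 0.43 | 0.60 | 0.78 |
| 0.75 | 0.43 | 0.69 | 0.93 |

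Both f and s are assumptions. The table shows direction and sensitivity, and is not an estimate for this trial.

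**The case against.** The range 9-23 also leaves out steps 1-8, which contain consent and eligibility, and no one would read it as waiving those for new subjects. It keeps steps 22-23, so the Day 14 visit and blood draw remain, and Table 2 makes no exception for later cohorts. This stands: a reader might infer that the plan means to drop Day 14 safety follow-up, and the documents do not support that. What survives is a conflict in an operational instruction.

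A reader might also infer that escalation proceeds without anyone looking. That is too strong. The range retains the questionnaire after stimulation, the second MRI and the telephone advice. Staff also work near the site afterwards. The TMS coil is positioned over each motor cortex at step 17, and the MRI Protocol places markers at the electrode centres during scanning. A seizure during the session would happen in front of staff. None of this is a graded skin check, so the gap is confined to the burn criterion.

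Neither the questionnaire nor vital signs form part of the major-response definition. Their omission leaves safety data incomplete but does not in itself alter the 3+3 decision. It would also be wrong to apply reduced detection to every major response, since the imaging criterion has its own scheduled scan.

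Finally, the symptom list is open-ended, the questionnaire and adverse-event forms are not in the documents, and Figure 4 is not shown. A burn item may exist on a form. The protocol text does not say so.

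**Conclusion.** The point holds in two limited parts and should be corrected.

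- **Conflict between passages.** Step 25 disagrees with Table 2 on the follow-up questionnaire, and the numbered steps disagree with Table 2 and Aim 1 on vital signs after stimulation. If staff followed step 25 literally and no cohort had to be expanded, Day 14 questionnaires would be missing for 15 of 18 subjects. If it is a slip, which is the likelier reading, nothing is lost beyond clarity.
- **Unspecified ascertainment.** A second degree burn can stop escalation, but how it is detected and graded after stimulation is not stated. Any burn-only event missed favours escalation. The magnitude cannot be determined from the documents.

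No stated sample size, error rate or power figure is affected.

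**What to change.** Reconcile step 25 and the numbered steps with Table 2, so that every cohort has the scheduled follow-up questionnaire and the vital signs after stimulation and at follow-up. If the range is meant to cover stimulation and follow-up, its end point must include step 24. The text should also make clear that new subjects complete steps 1-8.

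For the burn criterion, add one form entry giving the presence and degree of any scalp lesion, completed after stimulation and at the existing follow-up visit, with the person responsible named by role. Have the cohort review in step 25 use that entry, so that a finding of no major response rests on a recorded negative.

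The cost is protocol wording, one form line and a few minutes per subject. Currents, stopping rule, visits and sample size (3 to 36, with 18 predicted) are unchanged.
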